### **10.2 Inclusion / Exclusion Criteria (Aim 2 Debrief Interviews)**

#### **10.2.1 Inclusion/Exclusion Criteria (Aim 2)**

*Patients:* We will recruit a purposive sample of patient-participants from Aim 1 based on recording use (listened to none, one or all recordings; shared recording or not) and health literacy [SAHL-E score  $\leq 14$  (low health literacy) or  $> 14$  (high health literacy)].

PROTOCOL TITLE: *The impact of sharing audio recorded clinic visits on self-management in older adults: a multisite trial*

**Caregivers:** Patients will identify family members / caregivers who are 1)  $\geq 18$  years of age, 2) who can communicate in English or Spanish; and 3) have received access to the patient's audio recordings.

**Clinic staff:** We will include healthcare professionals and administrators who have been involved in the trial at each site including MDs, NPs, Nursing Staff, Medical Assistants, and Administrators.

## 11.0 Vulnerable Populations\*

- N/A.

## 12.0 Local Number of Subjects

A total of 30 patients and 6 clinicians will be recruited at each site (N=108). Based on prior work, we anticipate that a total of 60 patients will be approached to reach a sample of n=30 eligible patient participant patients at each site.

Hertzog estimated that a sample of 10 – 40 participants is adequate to detect feasibility issues and gather preliminary outcome data in a pilot project. With 30 patient participants and 6 clinicians per site (total sample, n=108) we will be able to estimate the operating diagnostics of a future study (e.g., retention rates) and approximate effect sizes with a satisfactory level of precision to 1) determine if a future study is feasible and 2) be able to accurately inform power and sample- size calculations for the future study. We are not powered to detect significant differences in outcomes.

## 13.0 Recruitment Methods

### 13.1 Recruitment procedures (Aim 1 Trial)

Identification of participants (Aim1): A standard procedure will be enacted at all study sites. We will identify a cohort of potentially eligible patients who have planned clinic visits with study clinicians. In line with privacy guidelines we will initially use the site-specific Data Warehouse which will identify potentially eligible patients of study clinicians who meet preliminary inclusion criteria, including age ( $\geq 65$  years) and diagnosis of hypertension and diabetes. Additional study data will also be extracted including: patient contact information (name, telephone - cell and home, email address, home address), sex, primary language spoken, existing diagnoses (dementia, Alzheimer's, Schizophrenia or other psychotic disorder, substance use disorder, deaf, blind), Charlson Comorbidity Index (each condition contributing to Charlson: present/absent), number of visits to study clinician in prior 7 months, scheduled visit dates in upcoming 6 months with study clinician, and current medications. We will also

PROTOCOL TITLE: *The impact of sharing audio recorded clinic visits on self-management in older adults: a multisite trial*

use the workbench feature of the Electronic Medical Record in order to generate lists of potential patients of study clinicians, and to check scheduled visits for recruited patients. A waiver of HIPAA Authorization has been applied for with the D-H Privacy Office. An RC in clinic, fluent in English (and in Spanish at our UTMB site where there is a significant portion of patients with Spanish as their preferred language), will review the scheduled appointment list for each upcoming month period from the EMR for patients who meet provisional eligibility criteria. This information will be transferred to a local REDCap Recruitment database for each site, which will only be accessible to IRB approved research staff at those sites. A list of potentially eligible patients will be sent to the study clinician for review, to ensure that they manage the patient's hypertension and diabetes medication. The study clinician will indicate any patients who do not meet the inclusion/exclusion criteria. Potentially eligible patients will receive a letter, signed by their clinician, informing them about the project, that they may be contacted by a member of a research team and offering them the opportunity to opt-out (by email or telephone). No less than two weeks after letters have been sent, an RA will contact patients by telephone to gauge their interest in the project. Patients will be given a number and email address to opt out of receiving a call. For those receiving a telephone call, the RC will briefly describe the project to the patient (Appendix. 9 Telephone Patient Recruitment Script): (1) their clinic visits during the study will be audio- recorded if they are randomly allocated to the AUDIO group for 3 months, or that they will continue to receive UC (an AVS); and (2) there will be a standard follow-up assessment for all study participants via telephone call or email at 1 week, and 3 months; additionally within one- week after any scheduled visit during the 3 month study period, the Interpersonal Processes of Care (IPC) Scale will be administered. Importantly it will be emphasized that willingness to get involved in the project will not affect their care and that no providers in the clinic are opposed to their patient participation. Interested patients will be asked screening questions to establish eligibility. We will gather minimal data on patients who fail screening (demographics, eligibility criteria failed). Patients who are eligible will be asked to arrive at clinic 30 minutes before their scheduled visit and will be reminded that the early arrival will not be indicated in appointment date/time reminders or MyChart/MyDH/MyHealthAtVanderbilt appointment times. Patients will also be sent a reminder letter/email/phone call prior to their scheduled visit (Appendix 10. Appointment Reminder Letter) and will also have the opportunity to complete eConsent and baseline assessment prior to the clinic visit (see Section 22).

*Identification of clinicians (Aim1).* Under the guidance of our clinic leads ( [REDACTED] [REDACTED] ) clinicians (MDs, NPs) have demonstrated an interest in taking part in the proposed project. Before the study commences, clinicians will receive an email from PI [name] (Appendix 21. Clinician Aim 1 Recruitment Email) and be invited to learn about the purpose of the study in a large group setting (routine conferences attended by associate providers, fellows and

PROTOCOL TITLE: *The impact of sharing audio recorded clinic visits on self-management in older adults: a multisite trial*

attendings and nursing staff meetings) or one-on-one including acknowledgment of support to conduct the study from clinic leadership and the intent to audio-record and share their clinic visits with patients. An opportunity to ask and answer questions about participation in the study will be provided.

We aim to recruit a minimum of 3 - 6 clinicians prior to the initiation of patient recruitment who will participate in both arms of the study. We will document the number of providers who are offered enrollment and the number who consent to participate in audio recordings. For clinicians who decline to participate in the study, we will anonymously document reasons for their refusal in a REDCap database. At the time of enrollment, we will ask providers to provide demographic information via survey including age, sex, race, ethnicity, years in practice and specialty (Appendix 11 Clinician Demographic Survey). Clinicians who enroll in the study will be offered the opportunity to participate in a brief semi-structured interview about their experience with recording when patient enrollment is complete (Appendix 12. Clinician Interview).

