## 4.0 Study Endpoints\*

### 4.1 Primary endpoint

The primary endpoints of this pilot trial are:

1) Feasibility: We will determine the optimal strategy to achieve a high retention rate and adherence to the study protocol. We will also assess retention rates (proportion of included patients completing T2 follow up; we will target >70%), fidelity to the study protocol (Borrelli et al criteria; we will target >90%) and the Feasibility of Intervention Measure (FIM, 4 items, see Appendix 1. 3-month Follow Up Assessment (T2); we will target an average score of >3).

2) Acceptability: We will determine the acceptability of the AUDIO intervention and study protocol by assessing the proportion of patients and clinicians who agree to take part in the project and proportion of patients who listen to the recording. Our primary indicator of acceptability will be the recruitment of 108 participants (N=30 patients and 6 clinicians per site) over our planned data collection period of six months. We will determine the listening rates (we will target >70%): this will include the proportion of patients in the intervention arm that log in to the online system and listen to (and how often) the recording. We will also document the number of patients who share or report sharing the recording and caregivers who access the recording. Participants will complete the Acceptability of Intervention Measure (AIM, 4 items, see Appendix 1. 3-month Follow Up Assessment (T2); target an average score of >3).

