## 6.0 Procedures Involved

**Study Design:** We will conduct a multi-site, two-arm, parallel group, patient-randomized, blocked, controlled, pilot trial with 3-month follow up, to determine the impact of sharing audio recordings of clinic visits (AUDIO) on self-management in older adults with diabetes and hypertension, compared to the AVS alone (Usual Care). We will recruit 108 adults (30 patients and approximately 6 clinicians per site),  $\geq 65$  years with diabetes and hypertension over a recruitment period of 3 months. We are primarily interested in determining the feasibility of the trial and acceptability of the AUDIO intervention. We will also explore the impact on the patients' ability to self-manage their care as well as exploratory outcomes, at baseline (T0 = pre-visit) and at regular intervals from enrollment (T1 = 1 week, T2 = 3 month). We will also adhere to the CONSORT Statement extension to randomized pilot and feasibility trials during the trial, publish a study protocol and register the study on ClinicalTrials.gov. Our decision to use a patient level randomized trial design is justified for several reasons: 1) randomization reduces the impact of selection bias and confounding; 2) the risk of contamination is low as audio recordings will be reviewed outside of the clinic and the information will be unique to the each patient; 3) individual-level randomization is more efficient than cluster (e.g. clinic) randomization; 4) the use of blocking further improves the statistical precision of results by ensuring that the key characteristics are balanced across treatment groups, avoiding reliance on statistical models to adjust for any imbalances and 5) we will set up routine evaluations of key operational features of the study design e.g., recruitment rates, intervention use, fidelity - determining the need to make changes/refinements to study procedures throughout the trial.

**6.1 Randomization process:** Patients will be randomly allocated to AUDIO or UC alone using a block-randomization technique with the clinician acting as the blocking variable. Blocks of 2 patients per clinician will be generated to ensure an equal number of patients per clinician will be randomly assigned to the AUDIO and UC arm. The

PROTOCOL TITLE: *The impact of sharing audio recorded clinic visits on self-management in older adults: a multisite trial*

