**Assessments:** A trained RA will collect data (**T0**= Baseline Assessment) by electronic tablet or by paper form if preferred by the patient prior to the visit. Patients who complete eConsent can also complete the baseline assessments via REDCap prior to the clinic visit. The PHQ-8 and GAD-7 will be administered after the clinic visit. Follow up is planned by email (Appendix 25 for the REDCap Survey Template) or telephone at **T1**= one week, **T2**= three months. For T1, the allowable window is up to two weeks from the scheduled timepoint. For T2, the allowable window is up to three weeks from the scheduled timepoint. Deviations from the follow up strategy (e.g., a patient who completes an assessment outside of the planned follow up window) will be reported to the IRB. No participant identifiers will be included on the labeling of study data. Study Unique ID code numbers instead of names will be used on participant materials, data and data-collection instruments to minimize risks regarding breach of confidentiality.

Patients will receive a printed schedule of follow-up assessments, tailored to times and days convenient to them.

Outside of the standard study follow up assessments, the patient will be met in clinic or contacted by email or telephone one week from any scheduled visit with a participating clinician to assess intervention use (AVS or AUDIO) and interpersonal processes of care (IPC) survey (immediately following the clinic visit, or within 1 week of the visit by email or telephone with the RA).

**6.4 Outcomes:** Our primary and exploratory outcome measures are outlined in Section 4.2 Table 1.

**6.4.1 Covariates:** Demographic information (age, sex, race, ethnicity, language used at home, educational attainment using categories from the 2016 American Community Survey) will be collected by the RA through patient report at enrollment. We will document if a caregiver (a support person, family member or friend) is present at the visit. We will collect demographic and practice information about participating clinicians including their age, sex, race, ethnicity and years in practice. The following covariates will be examined in our exploratory moderator analysis:

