**6.8 Debrief interviews (Aim 2):** Upon completion of the data collection for Aim 1, we plan to enroll participants for Aim 2. We will evaluate the acceptability of our study protocol and AUDIO intervention, barriers and facilitators to implementation of audio recordings through semi-structured interviews with patients, caregivers of intervention arm participants (a person who assists with the patient's care e.g. family member, friend) and clinicians at the three study sites: Dartmouth-Hitchcock Primary Care (Manchester, NH and Bedford, NH), Vanderbilt University Medical Center (Nashville, TN), and University of Texas Medical Branch, Internal Medicine - Geriatrics Clinic (Galveston, TX). We will select a sample of trial patient-participants (N=6), caregivers of intervention arm participants (N=6) and clinicians (N=6) at each site, for a total of 54 participants (18 patients, 18 caregivers, and 18 clinicians). In addition to this, we will plan to supplement our interviews with two additional Spanish language patient and caregiver participants at our UTMB site if the participants wish to take part. Given estimates that thematic saturation typically occurs between 12-18 interviews, we expect that our sample size for each stakeholder group (patients, caregivers, clinicians) will be adequate to achieve saturation of key themes.

**Study procedures:** Interview procedures will be similar across the stakeholder groups.

**PROTOCOL TITLE:** *The impact of sharing audio recorded clinic visits on self-management in older adults: a multisite trial*

When permission is granted, interviews (phone calls or in-person) will be conducted in a private area by a Research Assistant trained in qualitative methods and supervised by [name]. Interviews are expected to be 20-30 minutes in duration.

Interviews will be recorded using a digital recording device. These recordings will then be transcribed. When consent for recording is not granted, we will proceed with the interview and take detailed notes. If patients cannot be reached via telephone, an effort will be made to meet the patient at their next scheduled appointment to determine interest in continuing to that part in the project.

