### **13.2 Recruitment procedures (Aim 2 Debrief Interviews)**

*All interviewees will be recruited after their involvement in Aim 1 activities to eliminate the possible impact of the interview on outcomes.*

**13.2.1 Patients:** We will recruit a purposive sample of patient-participants who completed research activities in Aim 1 based on audio recording use and health literacy. At T2 follow up, the RA will assess the participant's interest in taking part in an interview about their experience with audio recordings. A list of patients who are interested will be compiled, from which we will identify patients to interview stratified by recording use and health literacy.

We will use the generated lists to identify potential patient interviewees. We will call by telephone or send a letter informing them that they have been selected for an interview. If a letter is sent, it will be followed by a telephone call to confirm interest and arrange a time and place to conduct the interview (Appendix 13. Patient Interview Guide). People interested in participating will meet with the research assistant at the clinic, office, or by telephone or videoconference to complete (Appendix 13b Patient Consent Form)

**13.2.2 Caregivers:** During telephone calls to patients from the AUDIO group, the RA will also explain that we would like to conduct interviews with caregivers who have received or listened to recordings from the patient. If the patient is willing to share the contact information of a caregiver (family member, friend) we will then contact them by a telephone call. We will inform the caregiver that the patient has given us permission to contact them about their experience using the recording. We will generate a list of interested caregivers stratified by recording use.

PROTOCOL TITLE: *The impact of sharing audio recorded clinic visits on self-management in older adults: a multisite trial*

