## 26.0 Multi-Site Research\*

This is a multi-site study that will involve 3 sites and a total of 30 patients and 6 clinicians recruited per site for a study total of N=108 participants (90 patients and 18 clinicians). All procedures (identification, recruitment, consent, data collection) described above will be followed at each site. REDCap will be used to gather, share and store data securely, across all sites.

Weekly meetings will be planned between the MPIs ([name], Dartmouth; [name], VUMC; and [name], UTMB).

**26.1 Organization structure.** Drs. [name], [name] and [name] will co-lead all aspects of the project: administrative, technical and scientific. We will complete and keep up-to-date the WORKSHEET: Communication and Responsibilities (HRP-830) and all PIs will be responsible for sharing the most current version of the protocol and consent documents with their study teams. [name] will serve as the Contact PI and will assume fiscal and administrative management and responsibility of the project. He will be responsible for communication with NIH and submission of annual reports. All PIs will be responsible for oversight of the project, including maintaining communication with

**PROTOCOL TITLE:** *The impact of sharing audio recorded clinic visits on self-management in older adults: a multisite trial*

each other, key personnel, and project staff through scheduled weekly meetings. Each PI will be the primary responsible party for all activities at their respective site. During weekly meetings, the PIs will meet with site coordinators to discuss study progress e.g., recruitment and retention rates, protocol adherence and data quality. Should concerns arise such as recruitment rates falling below target thresholds, mitigation plans will be generated and the trial steering committee will be informed and a meeting will be convened to determine if changes in protocol are required. Significant changes in protocol will be communicated with the IRB and approved. PI [name] will be responsible for creation of annual reports, publication of trial protocol on ClinicalTrials.Gov and coordination of manuscript and conference proceedings to emerge from the project, with support from both PIs [name] and [name]. Publication authorship will be based on the relative scientific contributions of project personnel. The Trial Steering Committee and MPIs will work together to identify lead, senior and contributing authors.

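### Section 13.1 offers clinicians the debrief interview at the close of enrollment, which contradicts the rule in 6.8 and 13.2 that interviewees are recruited only after Aim 1

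*Combined protocol and SAP*

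**What the plan says.** Section 13.1 (identification of clinicians) ends by saying that clinicians who enroll will be offered a "brief semi-structured interview about their experience with recording when patient enrollment is complete".

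Two other places set a later start:

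- Section 6.8, which names clinicians among the interviewees: "Upon completion of the data collection for Aim 1, we plan to enroll participants for Aim 2".
- The opening of section 13.2, which covers patients, caregivers and clinical staff: "All interviewees will be recruited after their involvement in Aim 1 activities to eliminate the possible impact of the interview on outcomes".

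Section 13.2.3, the Aim 2 text specific to clinical staff, gives no start point. Staff are emailed and choose a convenient time.

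On the trial calendar, section 6.0 plans to recruit "over a recruitment period of 3 months" and sets follow-up at "T1 = 1 week, T2 = 3 month". Section 4.1 (repeated in 17.1.2) expects to reach the recruitment target "over our planned data collection period of six months". Section 6.3 adds: "For T2, the allowable window is up to three weeks from the scheduled timepoint". Section 5.1.2 has later scheduled visits of AUDIO patients recorded and followed by the Interpersonal Processes of Care (IPC) survey. UC patients are offered the survey where possible, and one further scheduled visit per patient is expected in the 3 months.

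**The concern.** The close of enrollment is not the end of Aim 1. A clinician whose last patient has just enrolled still has recorded visits ahead, and still sees UC patients whose data count. IPC scores, service use and quality of diabetes and hypertension care are all still accruing.

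The interview asks about the acceptability of recording and about barriers and facilitators to its use. Held at that point, it could change how the clinician behaves at the remaining visits. Section 13.2 states a safeguard against that kind of influence, and 13.1 read literally bypasses it. The safeguard also governs when interviewees are recruited, so an offer made at the close of enrollment departs from it even if the conversation takes place later.

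There is a smaller cost to Aim 2 as well. An early interview would miss the clinician's experience of the remaining recorded visits.

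**Working it through.** **Inputs.** Patients and clinicians: "study total of N=108 participants (90 patients and 18 clinicians" (section 26.0). Follow-up F = 3 months (6.0). T2 window of 3 weeks (6.3). Recruitment length R = 3 months (6.0), or 6 months if the period in 4.1 is all recruitment. One further scheduled visit per patient (5.1.2). The documents do not state how many patients are in follow-up when enrollment closes, so that figure is derived here.

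**Plan's own total.** 3 sites × (30 + 6) = 108, of whom 3 × 30 = 90 are patients. This agrees with the plan.

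**Patients still before T2 when enrollment closes.** With even accrual (an assumption), the share is min(1, F/R).

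- R = 3: min(1, 3/3) = 1, so essentially 90 of 90. Because F is as long as R, this holds for any accrual pattern.
- R = 6: 3/6 = 0.50, so 45 of 90.
- R = 6, every patient using the full T2 window: F = 3 + 21/30.4 = 3.69 months, and 3.69/6 = 0.615, so about 55 of 90. This is an upper bound for even accrual.
- If the six months in 4.1 means 3 months of recruitment plus 3 of follow-up, the result is again essentially 90 of 90.

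**Sensitivity to accrual, R = 6, F = 3.** Let x = (6 − 3)/6 = 0.5 be the fraction of the recruitment period after which an enrolled patient is still in follow-up at close.

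- Linearly front-loaded: 1 − (2x − x²) = 1 − 0.75 = 0.25, or 22.5 of 90.
- Linearly back-loaded: 1 − x² = 0.75, or 67.5 of 90.

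**Visits still to come.** Behaviour can change only at remaining visits, so these are the closer measure of exposure. With even accrual, and the one expected visit spread evenly over follow-up, patients still in follow-up have half of it left on average:

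- R = 3: 90 × 0.5 = 45 visits.
- R = 6: 45 × 0.5 = 22.5, about 22 visits.

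About half of these would be in AUDIO, since allocation is balanced within clinician (6.1).

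**After the correction.** If the offer waits for the end of Aim 1 data collection, 0 of 90 patients are still in follow-up. That point falls 3 months after the last enrollment, or about 3.7 months with the full T2 window.

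**The case against.** The best reply is that the intended rule is already clear. Sections 6.8 and 13.2 are the Aim 2 text, and both put interviews after Aim 1. Section 13.2.3 sits under the rule that opens 13.2 and speaks of staff whose participation is past. The sentence in 13.1 is one line at the end of an Aim 1 recruitment paragraph, and it describes an offer rather than the interview. This stands as far as intent goes. A reader might infer that the plan is to interview clinicians mid-trial, and the documents taken together do not support that. But 13.1 is the only place that gives clinicians a milestone of their own, and a site could reasonably act on it.

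A reader might also infer that at least half the patients must still be in follow-up. That is certain only for 3-month recruitment. For 6 months it depends on the accrual pattern, and the share could be about a quarter.

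Finally, a reader might infer that the trial's results would be biased. Nothing in the documents shows this:

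- IPC and quality of care are exploratory outcomes, in a trial declared not powered for differences (12.0, 17.1.10).
- Recruitment, the leading indicator of acceptability, is finished by then.
- Clinicians treat patients in both arms, and section 17.1.9 relies mainly on comparisons within clinician and site. A general change in a clinician's manner would therefore tend to reach both arms.
- Clinicians already know about recording from consent and briefings, and the interview lasts only 20 to 30 minutes.

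These points limit the consequence. They do not reconcile the passages.

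**Conclusion.** Wrong as written: an internal contradiction of minor severity. Section 13.1 gives clinicians an earlier milestone than 6.8 and 13.2 allow, and 13.2.3 does not settle the matter. It is more than clerical, because it decides when a site approaches its clinicians and it concerns a safeguard that the protocol adopted for itself.

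At the earlier milestone, the number of patients still in follow-up is essentially all 90 with 3-month recruitment, or about 45 of 90 with 6-month recruitment and even accrual. The 25% to 75% range covers linear front- and back-loading only. The counts of remaining visits rest further on the plan's expectation of one more visit per patient and on even spacing. None of these figures measures bias. The effect of an early interview on outcomes is unknown.

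**What to change.** In 13.1, replace the end-of-enrollment timing with: *after Aim 1 data collection is complete (see 6.8 and 13.2)*. State the same start point in 13.2.3, so that the clinician-specific Aim 2 text carries its own date.

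A trigger tied to each clinician's own last T2 assessment would not match 6.8. It would let a clinician whose patients finish early be interviewed while Aim 1 data collection continues for others.

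The cost is an edit to two sentences. Clinician interviews begin about 3 to 3.7 months after the last enrollment, a wait that 6.8 already implies.
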